4.2 Number of Patients

The study will enroll up to 24 patients. The power calculation for efficacy is based on a sample size of 18 response-evaluable patients. The sample size was set to 24 to allow for enrollment of up to 6 patients who are not evaluable.

4.3 Number of Study Centers

This is a single-center study to be conducted at Huntsman Cancer Institute at the University of Utah, Salt Lake City, Utah.

4.4 Study Duration

The estimated duration of enrollment will be 30 months. The primary objective will be evaluated after 6 cycles of selinexor (cycle 7 day 1) treatment. Selinexor treatment will continue thereafter as long as the study drug is tolerated and subject does not meet discontinuation criteria. After discontinuation of the study drug, patients will be followed for survival. It is estimated that each patient will participate in the study for approximately 24 months. Therefore, the estimated study duration is about 60 months.

5 ELIGIBILITY CRITERIA

This eligibility checklist is used to determine patient eligibility and filed with enrolling investigator's signature in the patient research chart.

Patient No. _____

Patient's Initials: (L,F,M) _____

5.1 Inclusion Criteria

Yes/No (Response of "no" = patient ineligible)

- 5.1.1 Male or female subject aged \geq 18 years.
- 5.1.2 Eastern Cooperative Oncology Group (ECOG) performance status \leq 2
- 5.1.3 Diagnosis of primary myelofibrosis (PMF), post-essential thrombocythosis myelofibrosis (also known as thrombocythemia) (PET-MF) or post-polycythemia vera myelofibrosis (PPV-MF).
- 5.1.4 Life expectancy \geq 6 months.
- 5.1.5 Prior treatment with ruxolitinib or any experimental JAK1/2 inhibitor with any one or more of the following:
- Inadequate response after being on \geq 3 months of treatment defined by:
 - Palpable spleen \geq 10 cm below the left subcostal margin on physical examination at the screening visit OR
 - Palpable spleen \geq 5cm below the left subcostal margin on physical examination at the screening visit AND active symptoms of MF at the screening visit defined presence of 1 symptom score of \geq 5 or two symptom scores each of \geq 3 using the Screening Symptoms Form (Appendix 6)
 - Intolerant to ruxolitinib and/or other JAK1/2 inhibitors due to any grade \geq 3 non-hematologic AEs or any grade \geq 2 AEs requiring treatment discontinuation AND palpable spleen \geq 5cm below the left subcostal margin on physical examination at the screening visit.
- 5.1.6 Adequate organ function as defined as:
- **Hematologic** (\leq 28 days prior to C1D1):
 - Total white blood cell (WBC) count \geq 1000/mm³
 - Absolute neutrophil count (ANC) \geq 500/mm³
 - Hemoglobin \geq 7 g/dL
 - Platelet count \geq 30,000/mm³

For patients receiving transfusion and growth factor support, the following delays must be observed between the last administration and hematologic laboratory screening assessments:

- For hematopoietic growth factor support (including erythropoietin, darbepoetin, granulocyte-colony stimulating factor [G-CSF], granulocyte macrophage-colony stimulating factor [GM-CSF], and platelet stimulators [e.g., eltrombopag, romiplostim, or interleukin-11]): at least 2 weeks.

Growth factor support, RBC and/or platelet transfusions are allowed as clinically indicated per institutional guidelines during the study.

- **Hepatic** (\leq 28 days prior to C1D1):
 - Total bilirubin $< 1.5 \times$ ULN except in patients with indirect hyperbilirubinemia due to hemolysis or gilbert's syndrome where total bilirubin should be $< 5X$ ULN
 - Aspartate aminotransferase (AST) and alanine aminotransferase (ALT) $< 2.5 \times$ ULN.
- **Renal** (\leq 28 days prior to C1D1):
 - Estimated creatinine clearance (CrCl) ≥ 20 mL/min using the Cockcroft and Gault formula $[(140-Age) \times Mass (kg)] / (72 \times \text{creatinine mg/dL})$, multiply by 0.85 if the patient is female] OR

- 5.1.7 _____ Female patients of childbearing potential must have a negative serum pregnancy test (\leq 3 days prior to C1D1).
- 5.1.8 _____ Female patients of childbearing potential must agree to use 2 methods of contraception throughout the study and for 3 months following the last dose of study treatment (including 1 highly effective and 1 effective method of contraception as defined in section 7.4)
- 5.1.9 _____ Male patients must use an effective barrier method of contraception if sexually active with a female of childbearing potential.
- 5.1.10 _____ Recovery to baseline or \leq Grade 1 CTCAE v. 5.0 from toxicities related to any prior treatments including ruxolitinib or other experimental agents unless AE(s) are clinically nonsignificant and/or stable on supportive therapy.
- 5.1.11 _____ Able to provide informed consent and willing to sign an approved consent form that conforms to federal and institutional guidelines.

5.2 Exclusion Criteria

Yes/No (Response of “yes” = patient ineligible)

- 5.2.1 Prior exposure to a SINE compound, including selinexor.
- 5.2.2 Patients who are below their ideal body weight and would be unduly impacted by changes in their weight, in the opinion of the investigator, will be excluded.
- 5.2.3 Uncontrolled active infection requiring parenteral antibiotics, antivirals, or antifungals \leq 1 week prior to C1D1. Patients on prophylactic antibiotics or with a controlled infection \leq 1 week prior to C1D1 are eligible.
- 5.2.4 Radiation, chemotherapy, immunotherapy, or any other anticancer therapy (including investigational therapies) \leq 2 weeks
- 5.2.5 Ruxolitinib or other JAK1/2 inhibitors \leq at least 3 days or 5 half-lives prior to C1D1.
- 5.2.6 Major surgery \leq 4 weeks prior to C1D1.
- 5.2.7 Known active hepatitis A, B, or C infection; or known to be positive for hepatitis C virus ribonucleic acid (RNA) or hepatitis B virus surface antigen.
- 5.2.8 Any active gastrointestinal dysfunction interfering with the patient's ability to swallow tablets, or any active gastrointestinal dysfunction that could interfere with absorption of study treatment.
- 5.2.9 Any life-threatening illness, organ system dysfunction, or serious psychiatric, medical, or other conditions/situations which, in the investigator's opinion, could compromise a patient's ability to give informed consent, safety, or compliance with the protocol.
- 5.2.10 Contraindication to any of the required concomitant drugs or supportive treatments.
- 5.2.11 Subjects taking prohibited medications as described in Section 6.3. Following discontinuation of prohibited medications, a washout period is required prior to initiating study treatment (the duration of the washout must be as clinically indicated, e.g., at least five half-lives).
- 5.2.12 Subjects who are breastfeeding and unwilling to stop while on study.

I certify that this patient meets all inclusion and exclusion criteria for enrollment onto this study.

Investigator Signature

Date

Time

5.3 Recruitment Strategies

Potential patients will be identified by Investigators in the setting of their outpatient clinics.

6 TREATMENT PLAN

6.1 Administration Schedule

The schedule is based on 28-day cycles.

For patients enrolled after protocol version 7, Selinexor will be administered by oral route, beginning at 40 mg once weekly. Prior to protocol version 7, the starting dose of selinexor was 60 mg and 80 mg once weekly.

In case of toxicity at the starting dose level, dose modifications will be implemented as described in Section 7.1. Treating investigators may consider increasing the dose to 60 mg once weekly after 12 weeks of treatment in the absence of grade 2 or higher weight loss. The dose increase must be done after documented consultation with PI and medical monitor.

6.2 Selinexor

6.2.1 How Supplied, Stored, Packaged and Labeled

Selinexor will be provided by Karyopharm Therapeutics Inc. as coated, immediate-release oral tablets in strengths of 20 mg in wallet-sized blister packs which will be maintained by site Investigational pharmacy.

Selinexor 20 mg tablets are to be stored in a locked and secured area with access restricted to the site staff at room temperature (below 30 °C) in clear blister strips that are composed of either polyvinyl chloride (PVC)/polyethylene (PE)/polychlorotrifluoroethylene (PCTFE) clear film blister with a foil paper backing or (PVC)/(PCTFE)/(PVC) clear film blister with a foil paper backing. Room temperature storage is recommended, refrigerated is acceptable. Tablets should not be stored frozen.

The blistered packaged product will be placed in paperboard secondary packaging, to which labeling materials will be affixed.

All labels will include conditions for storage, lot number, and other information required by the Food and Drug Administration (FDA), International Council for Harmonisation (ICH), and/or Annex 13, as well as all local regulations for investigational medication.

Selinexor tablets are currently in on-going stability studies. The expiry will be based on concurrent stability studies and extended during the course of the study as further stability data becomes available.

6.2.2 Preparation and Administration

Qualified personnel, familiar with procedures that minimize undue exposure to themselves and the environment, should undertake the handling and safe disposal of selinexor in a self-contained and protective environment. No special preparation is required.

Selinexor should be taken with at least 120 mL (4 ounces) of fluids (water, juice, etc.) at approximately the same time each dosing day.

Selinexor tablets should be swallowed whole (not crushed) to prevent an increased risk of dermatologic toxicity if the powder comes in contact with skin. For doses of oral medications to be taken on non-clinic days, patients will be provided with medication to take home.

Missed Doses

If a dose was missed, the dose can be made up and the schedule should be altered to maintain at least 36 hours between two consecutive doses.

If a dose must be skipped (e.g., due to recommendation of treating physician), the next dose will be taken as per schedule. Doses should not be administered less than 36 hours apart and all missed and delayed doses should be documented.

Vomited Doses

If a dose is vomited within 1 hour of ingestion, it will be replaced. If vomiting occurs more than 1 hour after dosing, it will be considered a complete dose.

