2.3.3 Dose Schedule Rationale

Selinexor Dosing

Selinexor is approved for the treatment of adult patients with relapsed or refractory multiple myeloma who have received at least 4 prior therapies and whose disease is refractory to at least 2 proteasome inhibitors, at least 2 immunomodulatory agents, and an anti-CD38 monoclonal antibody.

In addition, selinexor is currently under investigation in ongoing Phase 1-3 trials in patients with various hematologic malignancies. In the phase 1 study dosing has safely reached 60 mg/m² (~100 mg) twice weekly (cleared DLT; total weekly dose 120 mg/m² [~200 mg]). The MTD has not been reached in this study, but two DLTs were observed at a dose of 85 mg/m² in a parallel ongoing study (KCP-330-002) of selinexor in patients with advanced solid tumors. Based on these findings, the MTD for selinexor in patients with B-cell malignancies

is 60 mg/m² twice weekly (120 mg per week or 480 mg per cycle). Among heavily pretreated patients enrolled in this ongoing Phase 1 trial, selinexor-related Grade 3-4 thrombocytopenia has been observed primarily at total weekly doses of \geq 46 mg/m² and Grade 3-4 neutropenia at total weekly doses \geq 60 mg/m². Overall, increased rates of infection associated with selinexor have not been reported, however greater incidences of sepsis were seen with selinexor vs. PC in elderly patients with RR AML receiving doses $>$ 60 mg of selinexor in study KCP-330-008. Going forward, selinexor will be administered primarily as fixed milligram doses, as analyses of Phase 1 PK data indicated that exposure is not strongly correlated with BSA. Based on tolerability, safety, efficacy, and DLT evaluations, the following doses are recommended as a single agent for current and future Phase 2 and 3 studies: 60 mg BIW in elderly AML, 60 mg BIW in NHL, and 80 mg BIW in multiple myeloma (in combination with dexamethasone 20 mg BIW). Selinexor in combination however is administered on a weekly schedule and at doses of 60-100 mg.

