To date, 12 patients with myelofibrosis were dosed with selinexor in this study. The starting dose of selinexor was 80 mg weekly in the first six patients. After 3 out 6 patients required dose reduction due to grade 2 weight loss. The starting dose of selinexor was decreased to 60 mg weekly for subsequent patients. Additional six patients were enrolled at starting dose of 60 mg weekly. Of all the 12 patients, 7 required dose reduction to 40 mg weekly. Grade 2 weight loss occurred in 5 of 7 patients that required dose reduction to 40 mg weekly. At this time, 4 patients remain on selinexor treatment, 2 on 60 mg weekly dose and 2 on 40 weekly dose. The starting dose of selinexor will be decreased to 40 mg weekly for the remaining 12 expected patients.

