6.2.3 Accountability and Compliance

Selinexor must be requested by submitting an order form directly to the drug depot and will be shipped directly to site's Investigational Drug Services.

The investigator, or a responsible party designated by the investigator, must maintain an adequate record of receipt, distribution, and return of all study drugs in the form of a Drug Accountability Form. Such records must be provided to the drug supplier upon request.

Subjects are required to bring all used packs and any unused investigational product (IP) when they visit to the site at the end of each cycle. Compliance will be assessed by discussion with the patient and confirmed by pill count. Any deviations and missed doses (including reasons for the deviation or missed doses) will be recorded in the site's internal database and drug accountability logs with the reasons for subsequent verification.

The IP returned by subjects or any unused IP (that is, never dispensed to any subject) must be destroyed after accountability has been performed and only after written authorization from Karyopharm Therapeutics, Inc. has been received.

Subject compliance with the treatment and protocol includes willingness to comply with all aspects of the protocol. The investigator will try to ensure complete compliance with the dosing schedule by providing timely instructions to the patients. In case of non-compliance, the patients will be instructed again. At the discretion of the principal investigator, a subject may be discontinued from the trial for non-compliance with follow-up visits or study drug.

Selinexor should not be used for any purpose outside the scope of this protocol, nor may selinexor be transferred or licensed to any party not participating in the clinical study. Data for selinexor are confidential and proprietary and shall be maintained as such by the investigators.

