Selinexor should be withheld in patients with suspected or active uncontrolled infections, grade 4 infections, or clinical sepsis (in the absence of documented infection). Selinexor treatment can be resumed after initiation of appropriate antimicrobial therapy and when the infection has clinically resolved and/or the patient is clinically stable. When ready to resume selinexor, treatment may continue at the original dose, even in the setting of continued antimicrobial agents.

Diarrhea

Diarrhea associated with selinexor is typically watery and low-grade and usually responds to treatment with standard anti-diarrheal agents (e.g., loperamide) and/or dose modification. Careful assessment of the patient's volume status is essential. Fluid replacement is important to prevent dehydration, fatigue and electrolyte abnormalities (e.g., hyponatremia).

Fatigue

Prevention of anorexia, vomiting, and dehydration may reduce fatigue. Also, as per NCCN Guidelines, the use of methylphenidate 5 mg QD each morning may be helpful. Hemoglobin levels must be optimized as anemia appears to contribute substantially to fatigue, particularly in patients with heavily pretreated hematologic malignancies. In patients with adequate antitumor control on selinexor, QW dosing is often associated with improvement in fatigue and other side effects.

Decreased Appetite

In patients with problematic food/liquid/caloric intake secondary to anorexia, a patient log of food and drink, as well as body weights, should be considered and monitored by site staff. Nutritional counseling is important. Dysgeusia may contribute to the anorexia, and dietary

adjustments can be helpful. Fresh juices and simple carbohydrates, as well as ginger-containing foods and beverages, can improve appetite; ginger-containing foods may also improve dysgeusia. Administration of high caloric beverages (e.g., Boost®, Ensure®) and appetite stimulating agent(s) should be instituted aggressively in patients who develop significant anorexia.

A combination of appetite stimulating agents, particularly olanzapine (2.5 to 5.0 mg every morning), and standard anti-emetics is usually effective in managing selinexor associated anorexia that does not respond to the above interventions. Megesterol acetate 400 mg daily may also be effective. Additional information on the management of anorexia is provided in the NCCN Guidelines.

Hyponatremia

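### Section 6.2.2 limits a made-up dose only by a 36-hour gap although every dose level is once weekly, so two full weekly doses may be taken as little as 36 hours apart (minor safety point)

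*Combined protocol and SAP*

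**What the plan says.** Section 6.1 gives the regimen for patients enrolled after version 7: "Selinexor will be administered by oral route, beginning at 40 mg once weekly". Table 3 in section 7.1 adds an escalated level of 60 mg and a reduced level of 20 mg, both once weekly. The study calendar (section 8) places doses on Days 1, 8, 15 and 22 of a 28-day cycle.

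For a missed dose, section 6.2.2 says that "the dose can be made up and the schedule should be altered to maintain at least 36 hours between two consecutive doses". A dose that has to be skipped, for instance on the physician's advice, is a separate case: "the next dose will be taken as per schedule". The paragraph ends by repeating the floor and adding a duty to record: "Doses should not be administered less than 36 hours apart and all missed and delayed doses should be documented". Section 6.2.3 adds: "Compliance will be assessed by discussion with the patient and confirmed by pill count".

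No other section sets a latest time for making up a dose, a longer gap, a maximum number of doses in 7 days, or a limit on how many missed doses may be made up.

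**The concern.** A 36-hour floor does not fit a drug taken every seven days. A patient who follows section 6.2.2 exactly can take two weekly doses a day and a half apart.

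What is at stake is tolerability. The starting dose has already come down twice, from 80 to 60 to 40 mg weekly. Sections 2.3.3 and 11.3.1 report that 3 of the 6 patients who started at 80 mg weekly needed a reduction for grade 2 weight loss (section 11.3.2 gives the number as 2). Section 2.3.3 then states: "Of all the 12 patients, 7 required dose reduction to 40 mg weekly". Section 7.2, under Fatigue, notes that in patients with adequate disease control "QW dosing is often associated with improvement in fatigue and other side effects".

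From cycle 2 the Day 8, 15 and 22 doses are taken at home, and from cycle 7 clinic visits are required only every three months (calendar footnotes 19 and 27). The written rule therefore matters more than it would if dosing were observed.

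**Working it through.** The plan states no figure to reproduce here, so the check is interval arithmetic on the dosing text.

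**Inputs.** Weekly dosing at 20, 40 or 60 mg (6.1, Table 3); doses on Days 1, 8, 15 and 22 (section 8); minimum gap 36 h (6.2.2); twice-weekly doses recommended in other diseases, "60 mg BIW in elderly AML, 60 mg BIW in NHL, and 80 mg BIW in multiple myeloma" (2.3.3).

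1. Scheduled gap: 7 × 24 = 168 h. The permitted minimum is 36/168 = 21.4% of it.

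2. A compliant close pair. The Day 8 dose is missed and taken 36 h before an on-time Day 15 dose. It falls 168 − 36 = 132 h (5.5 days) late, on about Day 13.5. The gap since Day 1 is 336 − 36 = 300 h (12.5 days).

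3. Size of the pair: 2 × 20 = 40 mg, 2 × 40 = 80 mg, 2 × 60 = 120 mg. Three doses are taken from Day 1 to Day 15, as planned, so the total is unchanged.

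4. Is 5.5 days the latest make-up? No. Section 6.2.2 lets the schedule move. A dose remembered 6 days (144 h) late comes 168 − 144 = 24 h before the next one. Moving that next dose by 36 − 24 = 12 h satisfies the rule. The current text sets no latest time.

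5. Comparison with other schedules in 2.3.3. Twice weekly at 60 or 80 mg totals 120 or 160 mg every week. A one-off 80 mg pair is 80/160 = 50% to 80/120 = 67% of that. A 120 mg pair is 120/160 = 75% to 120/120 = 100%. Against the roughly 200 mg per week that phase 1 reached, the pairs are 40% and 60%.

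6. Effect of a 72 h floor, as an illustration. The minimum gap becomes 72/168 = 42.9% of the interval. With the next dose fixed, the latest make-up is 168 − 72 = 96 h (4 days). Any dose remembered later than that is omitted. Six cycles hold 6 × 4 = 24 doses, so each omission is 1/24 = 4.2%, or 40 of 24 × 40 = 960 mg at the starting dose.

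7. Fit with the visit windows in section 8. Moving one Day 1 clinic dose by its window leaves at least 168 − 48 = 120 h to a neighbouring on-time dose in cycles 2 to 7 (2 days), and 168 − 72 = 96 h from cycle 10 (3 days). Neither falls below 72 h.

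The documents give no frequency for late doses, so the expected number of close pairs cannot be estimated.

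**The case against.** The evidence on tolerability is not about spacing. The reductions arose under sustained weekly dosing at 80 or 60 mg, whereas a made-up dose replaces a missed one. Section 7.2 does not separate spacing from total dose. Section 2.3.3 recommends 60 to 80 mg twice weekly in other diseases, so doses a few days apart are ordinary use of this drug. Late doses are documented and discussed with the patient, non-compliant patients are instructed again, and Table 4 governs any toxicity. A 72 h floor has no more support in the documents than 36 h and still allows two doses within 7 days.

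Most of this stands, and it is why the point is minor. Two replies remain. The twice-weekly recommendations come from other diseases, and in this trial 80 mg once weekly was already poorly tolerated. A pill count shows the number of tablets taken, not their spacing, so only the discussion and the record of delayed doses would reveal a close pair, and only afterwards.

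Some stronger readings are tempting. A reader might infer that the rule allows doses closer than 36 hours. It does not: 36 hours is the permitted minimum. A reader might infer that the rule raises exposure or has been shown to cause harm. Total dose is unchanged, and the documents report no event from a close pair. A reader might also note that section 2.3.3 places grade 3-4 thrombocytopenia mainly at weekly totals of 46 mg/m² or more. At its conversion of 60 mg/m² to about 100 mg, that is 46 × 100/60 ≈ 77 mg, which an 80 mg pair exceeds. But that figure describes total weekly doses in heavily pretreated phase 1 patients, not a single pair after a missed dose, so it makes the concern plausible without demonstrating it.

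**Conclusion.** The point holds as a minor safety correction. The make-up rule allows two full weekly doses as little as 36 hours apart, 21% of the scheduled interval, totalling 40, 80 or 120 mg. It has no bearing on sample size, alpha, power or total dose. The likely safety gain is small and cannot be quantified from the documents.

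The conclusion rests on the literal text of 6.2.2 and on the absence of any longer gap or cut-off elsewhere. Patient instructions outside these documents might be stricter.

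A reader might infer from the arithmetic that 5.5 days is the latest make-up under the current text, or that a 72-hour rule would affect only doses 4 to 5.5 days late. Neither follows, because the present rule lets the next dose move. A 72-hour rule with a fixed next dose affects every dose remembered more than 4 days late.

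**What to change.** Replace both 36-hour sentences in 6.2.2 with a rule along these lines:

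- A missed dose is made up only if the next scheduled dose is at least 72 hours away.
- Otherwise it is skipped and the next dose is taken on schedule.
- No more than one missed dose is made up before the next scheduled dose.
- All missed, skipped and delayed doses are documented. (This keeps the duty that now sits in the second 36-hour sentence.)

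The 72 hours is an assumption with no source in the documents, and the sponsor should choose the figure. If the intent is never more than one dose in 7 days, the rule should instead say that the dose after a late one is taken 7 days later. It must then say what happens to the next Day 1 clinic dose when the shift exceeds its visit window. Patient instructions should be aligned either way.

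Costs: with 72 hours, any dose remembered more than 4 days late is lost (4.2% of the six-cycle total each time), and so is the present option of shifting the next dose. The text is one paragraph, but section 15.11 requires IRB approval. Section 15.4 may also bring in DSMC review and PRMC approval if the edit counts as a change in dosing.
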